8.1.2. Predicted site and patient recruitment for pilot phase

	Month	# Sites open	# Recruits per month	Cumulative total recruited per month
	Nov-21	1	0	0
	Dec-21	3	17	17
se	Jan-22	6	37	52
Phase	Feb-22	9	51	105
Pilot I	Mar-22	9	52	157
Pil	Apr-22	12	70	227
	May-22	12	70	297
	Jun-22	12	70	367
	Jul-22	12	70	437

RAG Criteria:

- *Green Light:* If all green criteria are met, we will proceed to a full trial with the protocol unchanged (unless there is a clear message from the process evaluation that would improve the protocol).
- Amber Light: If one or more of amber criteria are met, we will adapt the protocol with feedback from the Process Evaluation and our experience; and assess whether adaption of the protocol requires an extension of the internal pilot and further feasibility study. This plan was supported strongly by the Intrapartum Care Clinical Study Group.

• *Red Light:* If one or more of these criteria are met, we would discuss with the Trial Steering Committee whether proceeding with the trial is feasible.

Qualitative process evaluation data

We will collect data to explore the feasibility, acceptability and appropriateness of the trial processes (including consent) and interventions for women and healthcare professionals, in order to support and inform decision-making around progression to a full trial.

8.2. Main Trial Outcomes

8.2.1. Primary Outcomes

These will be recorded after birth by the accoucheur or attending midwife using a dedicated CRF on the day of the birth/delivery – Day zero (D0).

1. Third/forth degree perineal trauma involving anal sphincter complex diagnosed on clinical vaginal/rectal examination after birth (superiority co-primary outcome)

Identification will be by clinical examination as this is a pragmatic study; the principles of diagnosis will be refreshed at the site-specific trial education visit.

Adherence to the principles of diagnosis will be collected as Process Data.

2. Caesarean section (non-inferiority co-primary outcome)

8.2.2. Secondary Outcomes

NEONATAL

Severe neonatal trauma and morbidity - at neonatal discharge (captured on the neonatal CRF)

- Composite: After discussion between the perinatal outcome experts in the study team and PPI advisers, we propose a composite safety signal outcome, for what would be rare neonatal events, to summarise the potential adverse outcomes for the baby. We have aligned with the outcome designed in the national Birthplace in England Research Programme [28]. The ROTATE composite outcome is assessed at discharge from hospital and comprises any of:
 - o stillbirth after study entry
 - early neonatal death (≤7 days)
 - evidence of intrapartum hypoxia (Apgar score ≤7 at 5 minutes after birth)
 - the presence of neonatal encephalopathy receiving treatment with therapeutic hypothermia
 - neonatal seizure(s)
 - o meconium aspiration syndrome
 - o brachial plexus injury, fractured humerus or fractured clavicle

These reflect the potential outcomes relating to intrapartum hypoxia and potential trauma from a physically difficult birth and meet the target of a "take-home healthy baby" as identified by our wider PPI activities including the new lay PPI panel. All are relatively rare events hence the use of a composite measure, but we anticipate a higher rate compared to that found in the Birthplace study (4.4 (95% CI 3.3 - 5.9) per 1000 deliveries in obstetric units), in which women were all of low risk (25).

• Individual Outcomes: Each component of the neonatal composite outcome will also be reported separately.

PROCESS DATA - SOON AFTER BIRTH (D0)

Completed by the accoucheur or attending midwife (D0 CRF):

- Position of the fetal head (right occiput anterior (ROA) occiput anterior (OA), left occiput transverse (LOT), direct occipito-anterior (DOP), etc) before rotation (at diagnosis) using a pre-formatted ROTATE diagram (clock).
- Use of ultrasound to diagnose position before rotation: Yes/No
- Position of the fetal head at birth using a pre-formatted ROTATE diagram (clock) NB: If rotation to a direct occipito-posterior position took place, whether accidentally or on purpose (binary).
- Position of the ventouse cup, using a pre-formatted ROTATE diagram (flexing median, deflexing median, flexing paramedian, deflexing paramedian).
- Forceps marks on the baby :
 - Right blade (normal, over >50% orbit, not reaching jaw)
 - Left blade (normal, over >50% orbit, not reaching jaw)
- Adherence to all key steps of the manual rotation process using a dedicated ROTATE checklist supported by pictures from the ROBuST manual. (Yes: all tick-boxes / No: partially/none)
- Adherence to standardised assessment of the primary outcome (anal sphincter injury) (Supported by pictures) using a dedicated study checklist (Yes: all tick-boxes / No: partially/none)

MATERNAL - SOON AFTER BIRTH (D0)

- Vaginal birth after successful rotation with first allocated method (manual or instrumental rotation) (D0 CRF).
- Change from rotational ventouse to rotational forceps (both rotational ventouse and rotational forceps are in the same trial arm). This change will be recorded and measured as an important event (D0 CRF).
- Severe/complex 2nd degree vaginal tears and/or cervical tears (Y/N) any of: cervical, spiral, multiple, bilateral, high, or requiring complex suturing as determined by the accoucheur (D0 CRF).

MATERNAL - AT DISCHARGE/48 HOURS (whichever sooner)

- Estimated blood loss following birth up to 24 hours after birth so as to capture only primary haemorrhage (continuous variable). Need for blood transfusion (including use of cell salvage): Any red blood cell (RBC) blood transfusion or cell salvage of ≥ 300mls commenced any time between randomisation and 48 hours after birth (or hospital discharge if earlier than 48 hrs) (Y/N)
- Breast-feeding: Any breastfeeding, defined in accordance with the UK Infant Feeding Survey 'as infant being breastfed (including being given expressed breastmilk), within the past 24 hours, even if they are also receiving infant formula, solid food or other liquids'.
- Maternal Experience:

Childbirth Experience Questionnaire (CEQ)

The CEQ has 22 statements assessing four domains of childbirth experience (27). For 19 of the items the response format is a 4-point Likert Scale and three of the items

are assessed using a visual analogue scale (VAS). Higher scores indicate better childbirth experience.

Client Satisfaction Questionnaire-8 (CliSQ)

The CliSQ (28) is an 8-item questionnaire which measures three aspects of satisfaction: environment condition, care procedures and provided education. Total scores are converted into percentages and bands of 0–39, 40–59 and 60–100 are used to represent dissatisfaction, neutral, and satisfaction respectively.

MATERNAL - AT 3 MONTHS AFTER BIRTH (+ 7 days)

- Breast-feeding (CRF): Any breastfeeding, defined in accordance with the UK Infant Feeding Survey 'as infant being breastfed (including being given expressed breastmilk), within the past 24 hours, even if they are also receiving infant formula, solid food or other liquids'.
- Maternal Experience (same questionnaires as at Discharge/48h: CEQ, CESQ-8)
- •
- Urinary incontinence:
 - ICIQ (International Consultation on Incontinence Questionnaire) score (29).
 - The questionnaire has 4 Question items:
 - Frequency or urinary incontinence
 - Amount of leakage
 - Overall impact of urinary incontinence
 - Self-diagnostic item (not scored)
 - Scoring scale: 0-21 total
- Faecal incontinence:
 - Fecal Incontinence Quality of Life Scale (30)
 - The questionnaire is composed of a total of 29 items; these items form four scales:
 - Lifestyle (10 items),
 - Coping/Behaviour (9 items),
 - Depression/Self-Perception (7 items)
 - Embarrassment (3 items).
 - Items are scored 1-4 and averaged (total score is 4-16 with no cut-off).
- PTSD symptoms:
 - CITY Birth Trauma Scale (31)

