Pragmatic, multicentre, 2-arm parallel group, open-label, randomised controlled trial with an internal pilot and qualitative process evaluation.

Participant Population and Sample Size

Women at full cervical dilatation (second stage of labour) with persistent malposition of the fetal head. A total sample of 5,200 women from approximately 40 sites.

Setting

NHS consultant-led maternity units in the UK

Eligibility Criteria

Inclusion Criteria:

- ≥16 years of age at time of randomization
- Singleton pregnancy
- ≥36 weeks' gestation with cephalic presentation and persistent malposition of the fetal head occiput between 2 and 10 o'clock (diagnosed clinically or with ultrasound) requiring a rotational operative vaginal birth conducted or supervised by obstetricians signed-off as competent in both manual and instrumental rotation.

Exclusion Criteria:

- Women with contraindications for operative birth with either ventouse or forceps
- Women with fetal occiput between 11 and 1 o'clock
- Brow presentation;
- Intrauterine fetal death

Interventions

Manual rotation and instrumental rotation (either forceps or ventouse depending on practitioner preference) allocated on a 1:1 ratio.

Outcome Measures

Primary

- Third/forth degree perineal trauma involving anal sphincter complex diagnosed on clinical vaginal/rectal examination after birth (superiority co-primary outcome).
- Caesarean section (non-inferiority co-primary outcome).

Secondary:

- Successful vaginal delivery with first method.
- Severe neonatal trauma and morbidity.
- Cross-over (instrumental rotation after failed manual rotation; or manual rotation after attempted instrumental rotation).
- Breast feeding intention after birth, at hospital discharge and at 3 months post randomisation.
- Estimated blood loss following birth.
- Need for blood transfusion (or use of cell salvage) before hospital discharge.
- Urinary incontinence at 3 months post randomisation.
- Other major maternal morbidity within 3 months post randomisation, including faecal incontinence
- Maternal experience (Childbirth Experience Questionnaire) and satisfaction (Client Satisfaction Questionnaire-8) at discharge and 3 months post randomisation.
- Post-traumatic stress disorder (PTSD) symptoms at 3 months post randomisation.

Qualitative Process Evaluation

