1.2. Trial Rationale

Making birth safer to prevent poor outcomes for mothers and their babies is now a national priority within the NHS Long Term Plan, with an explicit ambition to halve rates of maternal deaths and babies' brain injuries occurring during or soon after birth, stillbirths and neonatal deaths by 2025 (8). Despite those initiatives severe perineal tearing has risen from 1.8% in 2000 to 5.9% in 2011 among first-time mothers (9).

It is important to investigate approaches to reduce maternal and neonatal morbidity arising from assisted delivery. The risk for mothers and babies is increased if more than one technique or more than one instrument is used to deliver babies with malposition. Failure in achieving a vaginal delivery leads to caesarean section which can also increase maternal and neonatal morbidity. The proportion of caesarean births is also increasing across the NHS - between 2010 and 2015 the increase was 2.4% in England and 4.7% in Scotland (10). Caesarean section in labour, and particularly during the second stage of labour, is considered high risk for both mother and babies with substantially increased rates of maternal haemorrhage, additional uterine lacerations, and neonatal trauma (11). Caesarean section in the second stage of labour also has long term consequences such as increased risk of preterm birth in the subsequent pregnancy (4–7) as well as increased risk of uterine rupture, caesarean hysterectomy, and morbidly adherent placenta (12). A recent series published in the Lancet identified that equipping clinicians with confidence and skills for safe and effective vaginal birth is a key intervention for preventing unnecessary intervention and for optimising caesarean section use, whilst reducing maternal and neonatal morbidity (12–14). A International Federation of Gynecology and Obstetrics (IFGO) position paper, published alongside the series, identified the appropriate use of instrumental birth in the second stage of labour (fully dilated cervix), as one of six priorities (15).

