9. TRIAL PROCEDURES

9.1. Schedule of assessments

Assessment		Screening	Day 0	48 hours (or maternal discharge if sooner)	Neonatal Discharge	3 months ±7 days
Eligibility check		x	х			
Valid informed consent			Verbal	x ¹		
Randomisation			х			
Co-primary Outcomes	Anal sphincter injury		x			
	Caesarean		х			
Neonatal Composite & Components					x	
Assessment of Adverse Events				x	x	x
Process Outcomes	Use of ultrasound to diagnose position before rotation	x				
	Position of fetal head before rotation	x				
	Position of fetal head at birth		х			
	Position of the ventouse cup		x			
	Forceps marks on the baby (diagrams)		x			
	Adherence to key steps of the manual rotation process		x			
	Adherence to standardised assessment of the primary outcome		x			
Maternal	Vaginal birth after successful rotation with the first instrument		x			
	Change from rotational ventouse to rotational forceps		x			
	Severe/complex 2 nd degree vaginal/cervical tears		x			
	Breastfeeding (UK Infant Feeding Survey)			x		x
	Estimated blood loss			x		
	Need for red blood cell transfusion (or use of cell salvage)			x		
	Urinary Incontinence ICIQ Fecal Incontinence Quality					x x
Maternal Experience	of Life Scale Childbirth Experience Questionnaire (CEQ)			x		x
	Client Satisfaction Questionnaire (CliSQ)			x		x
Maternal PTSD symptoms	CITY Birth Trauma Scale					x

¹ Where participants do not give written consent routine clinical data will be collected on the Day 0, 48 Hour Follow Up and Neonatal CRFs only

Any paper CRFs should be submitted upon completion. Quality of life questionnaires may be emailed directly to participants for completion if they are not in hospital at the assessment timepoint; or may be completed over the phone with the research midwife.

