14.2.2. Secondary outcomes

Analysis will be performed as per the primary outcome for all binary secondary outcomes (e.g. successful vaginal birth, breastfeeding intention after birth) as well as any safety output (e.g. SAEs). For continuous outcomes (e.g. estimated blood loss), a mixed-effects linear regression model will be used to generate difference between group means and confidence intervals adjusting for the same minimisation parameters as the primary outcome.

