14.2.5. Missing Data and Sensitivity Analyses

Every attempt will be made to collect full follow-up data on all study participants; it is thus anticipated that missing data will be minimal. Participants with missing primary outcome data will

not be included in the primary analysis in the first instance. This presents a risk of bias, and sensitivity analyses will be undertaken to assess the possible impact of the risk.

Per protocol, populations are 1) women having manual rotation as the first method, 2) women having instrumental rotation as the first method (regardless of instrument used). As we anticipate some cross-overs for participants having a failed attempt at rotation with one method to the other (instrumental rotation after failed manual rotation; and manual rotation after instrumental rotation), we will examine the robustness of the conclusions using appropriate sensitivity analyses including a per protocol analysis (i.e. restricting the analysis data set to those women who received the allocated intervention only) on the two co-primary outcomes. In two recent studies (16,17) the rate of cross-over was 0% after rotational forceps, and 0.6% (1/163) after manual rotation, representing a single case in one study (17). In the same study (17), although a second instrument was used in 36.9% of cases after rotational ventouse, this typically involved the use of forceps to complete the birth and therefore was not a cross-over from ventouse to manual rotation . Therefore, we expect the rate of cross-over between the two intervention groups to be very low – the 95% confidence interval for a rate of 1/163 is: 0.01 to 3.37%.

Full details will be included in the Statistical Analysis Plan.

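### The ventouse-to-forceps secondary outcome can in practice occur only in the instrumental arm yet falls under the between-arm model, and two-way cross-over is missing from the detailed outcome list

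*Protocol*

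**What the plan says.** The Trial Summary, under secondary outcome measures, includes "Cross-over (instrumental rotation after failed manual rotation; or manual rotation after attempted instrumental rotation". This is defined for both arms.

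Section 8.2.2 does not list it. In the maternal block for the day of birth, the only item on a sequence of techniques is "Change from rotational ventouse to rotational forceps (both rotational ventouse and rotational forceps are in the same trial arm", and the protocol adds: "This change will be recorded and measured as an important event (D0 CRF". The schedule in 9.1 also has no cross-over row. It carries "Change from rotational ventouse to rotational forceps" among the maternal outcomes, apart from the process outcomes.

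Section 14.2.2 then states: "Analysis will be performed as per the primary outcome for all binary secondary outcomes". The primary-outcome method in 14.2.1 is a mixed-effects log-binomial model giving relative risks and risk differences between arms. Its first fallback is Poisson regression with robust errors, and its second is an unadjusted log-binomial estimate.

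On frequency, 14.1 expects cross-over to the opposite method in under 1% of women. Section 14.2.5 supports this from earlier studies: "the rate of cross-over was 0% after rotational forceps, and 0.6% (1/163) after manual rotation".

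**The concern.** Two things do not fit together.

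First, the item in 8.2.2 describes a change between two instruments that belong to the same arm. A between-arm relative risk needs both arms to be able to produce the event by following their allocation, and the manual arm cannot. If 14.2.2 is applied as written, the results table will contain either a model failure or an extreme ratio. A reader could take that ratio as evidence against instrumental rotation when it only reflects how the event was defined.

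Second, the outcome that does apply to both arms, two-way cross-over, stands in the summary but has dropped out of the detailed list and the schedule. The statistician who builds the analysis from 8.2.2 will leave it out; one who builds it from the summary will include it. Section 1.2 gives the question substance, because it says risk rises if "more than one technique or more than one instrument is used to deliver babies with malposition". As 8.2.2 stands, the detailed list offers no direct two-arm comparison of how often a second rotational technique was needed.

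**Working it through.** **1. Reproduce the protocol's cross-over figure.** 1/163 = 0.61%. The exact (Clopper-Pearson) 95% interval is 0.016% to 3.37%. Section 14.2.5 prints 0.01 to 3.37%; the upper limit agrees, and the lower is truncated rather than rounded, which is immaterial.

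**2. Expected events by arm.** Let N = 2,600 per arm (14.1), c = proportion of the manual arm that crosses over, s = share of instrumental rotations that start with ventouse, and v = proportion of ventouse starts that change to rotational forceps. The documents give neither s nor v, so both are assumptions.

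- Instrumental arm: N × s × v. With v = 5% and s = 25%, 50% or 75%, this gives 32.5, 65 or 97.5 women. Letting v run from 1% to 10% widens the range to 2,600 × 0.25 × 0.01 = 6.5 up to 2,600 × 0.75 × 0.10 = 195.
- Manual arm: N × c × s × v. With c = 0.61%, v = 5% and s = 50% to 100%, this gives 2,600 × 0.0061 × 0.5 × 0.05 = 0.40 up to 0.79 women. With c at the upper limit of 3.37%, it gives 2.2 to 4.4.

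**3. What the relative risk would estimate.** If ventouse share and change rate are the same in cross-overs as in the instrumental arm, the ratio manual/instrumental is (N × c × s × v) / (N × s × v) = c. The relative risk is then simply the cross-over rate: 0.0061 at the quoted figure, 0.034 at its upper limit, below 0.01 on the expectation in 14.1. It says nothing about the techniques, whatever s and v are.

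**4. Chance of an empty cell.** Treating the manual-arm count as Poisson, the chance of no events is exp(-0.40) = 67% or exp(-0.79) = 45% at the quoted cross-over rate. With a zero cell the log relative risk is not finite. Neither fallback in 14.2.1 cures this, because the Poisson and the unadjusted log-binomial models meet the same zero. A risk difference would still exist, but it would be close to minus the instrumental-arm rate.

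**5. Stress test.** Manual-arm women could also reach the event if they were given an instrument first. The lower edge of the amber adherence band in 8.1.1 is 90%. Setting c = 10% gives 2,600 × 0.10 × 0.5 × 0.05 = 6.5 expected events and a ratio of about 0.10. The model would then fit, but every manual-arm event would be in a woman who had left her allocation.

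**6. The lists side by side.**

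| Item | Trial Summary | 8.2.2 | 9.1 |
|---|---|---|---|
| Two-way cross-over | yes | no | no |
| Ventouse-to-forceps change | no | yes | yes |
| First-method success | yes | yes | yes |

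**7. Data available.** Section 7.5 records the first and second rotational technique with reasons. Section 11.1 lists first and second rotational method, and one method for delivering the baby after rotation. The gap is therefore in the outcome list; the rotational sequence itself is captured.

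**The case against.** The protocol itself discloses that the two instruments share an arm, so the item can be read as a within-arm record that complements cross-over. Section 14.2 calls itself an outline and leaves detail to the analysis plan, which could well report the item descriptively. Cross-over is also not neglected: 14.1 promises close monitoring and a sensitivity analysis without cross-overs, and 14.2.5 adds a per-protocol analysis. First-method success is defined for both arms and partly reflects failure of the first technique.

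Much of this stands, and it limits the point. It does not remove it. The item sits among the maternal secondary outcomes and not among the process data, and 14.2.2 covers all binary secondary outcomes without exception. First-method success does not separate caesarean section from a second rotational technique. Sensitivity and per-protocol analyses exclude or restrict women; they do not report second-technique use as an outcome.

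Three stronger readings are tempting, and the documents do not support them.

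- A reader might infer that the ventouse-to-forceps item is the protocol's chosen measure of the multiple-instrument risk in 1.2 and fails at that task. No section makes that link. Nor does 1.2 name multiple instruments as the mechanism behind both co-primary outcomes; it speaks of risk to mothers and babies in general.
- A reader might combine an assumed ventouse share with the statement that "although a second instrument was used in 36.9% of cases after rotational ventouse, this typically involved the use of forceps to complete the birth" and conclude that a specific, large number of second-instrument events is missed. The figure comes from one cited study, the ventouse share is not given, and the documents do not say how much of that use was planned completion of the birth. No count of missed events can be claimed.
- A reader might infer that nothing in the protocol compares the arms on this. First-method success partly does, and the summary's cross-over outcome would do so fully for rotation.

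**Conclusion.** The point holds in two parts. As 14.2.2 is worded, the ventouse-to-forceps item would be given a relative risk that cannot be estimated or is uninformative. This rests on the protocol's own cross-over expectation; the event counts also need the assumed values of s and v, but the conclusion does not, because the ratio reduces to the cross-over rate provided both are similar in cross-overs and in the instrumental arm. The event is not strictly impossible in the manual arm, but it is confined there to women who left their allocation. The contradiction between the summary on one side and 8.2.2 and 9.1 on the other is a matter of text and needs no assumption.

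The consequence is limited to secondary reporting. The sample size, the power and both co-primary analyses are untouched. It is worth correcting because it changes what will be reported and the correction is cheap.

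**What to change.** 1. In 8.2.2 and 14.2.2, state that the ventouse-to-forceps change is reported descriptively within the instrumental arm (number and percentage, with ventouse starts as the natural denominator) and is outside the between-arm model.
2. Restore two-way cross-over to 8.2.2 and 9.1 so that they agree with the Trial Summary. Report alongside it, in both arms, whether any second rotational technique was used, derived from the first and second rotational method fields in 7.5 and 11.1. Cross-over alone may be sparse: at 0.61% it is 2,600 × 0.0061 = about 16 manual-arm women. Counts should therefore accompany any modelled estimate.
3. Optional: if the Day 0 CRF is given a second traction entry, also count a change of traction instrument in both arms, leaving out the planned completion step after a successful rotation.

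Items 1 and 2 cost only protocol wording and need no new data. Item 3 needs a CRF change and can be recorded only from the time it is made; the first two do not depend on it.

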1. BACKGROUND AND RATIONALE

1.1. Background

Babies in labour tend to face maternal spine at the time of delivery (anterior position). Malposition of the fetal head affects one in twenty-five women (1) at full dilatation (second stage of labour) – about 30,000 per year in the UK. Malposition is a risk factor for failed vaginal birth requiring a caesarean section, and for trauma to mother and baby. Examples of malposition include transverse (baby faces mother's left or right side) and posterior position (baby faces mother's abdomen: 'back-to-back' position).

It is important to investigate if manual rotation will reduce the risk of severe trauma to a woman's perineum, specifically 3rd/4th degree perineal trauma involving the anal sphincter, and if it will increase caesarean section rate.

Severe perineal trauma has long-term consequences for the woman; studies have reported incontinence in more than 50% of women (2) and reduction of life quality (3).

Caesarean section at full dilatation, however, is a risky procedure for mothers and babies and can cause preterm birth in future pregnancy (4–7).

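### Faecal incontinence at 3 months is a stated outcome, but the protocol describes only a quality-of-life scale without a cut-off, so no rate of incontinence per arm is defined

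*Protocol*

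**What the plan says.** The secondary outcomes in the Trial Summary include "Other major maternal morbidity within 3 months post randomisation, including faecal incontinence". Section 8.2.2, under maternal outcomes at 3 months, has a faecal incontinence entry with one instrument, "Fecal Incontinence Quality of Life Scale (30", which is reference 30. It is described thus: "The questionnaire is composed of a total of 29 items; these items form four scales". The scales are "Lifestyle (10 items", "Coping/Behaviour (9 items", then Depression/Self-Perception with 7 items and Embarrassment with 3. The scoring line reads "Items are scored 1-4 and averaged (total score is 4-16 with no cut-off".

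The schedule in section 9.1 ("Fecal Incontinence Quality" and its continuation line) and the source data list in section 11.1 name the same scale and no other faecal or anal incontinence measure. The targeted adverse events in section 10.3 are delivery events and do not include incontinence.

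For urinary incontinence, section 8.2.2 specifies the ICIQ, with items on frequency, amount of leakage and overall impact, an unscored self-diagnostic item, and a total of 0 to 21.

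Section 14.2.2 analyses binary secondary outcomes by the primary outcome's model and continuous ones by a mixed-effects linear model that gives a difference in means.

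**The concern.** The outcome's label names a condition that a woman has or does not have. The measure named for it describes how a bowel problem affects daily life, coping, mood and embarrassment. The two are related but not the same, and the protocol gives no rule for getting from one to the other.

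This matters because faecal incontinence is the patient-reported outcome closest to the superiority co-primary, injury to the anal sphincter. Section 1.1 explains the importance of severe perineal trauma partly by a proportion: "studies have reported incontinence in more than 50% of women". A woman or a guideline group reading the results would look for a matching proportion by arm and would find a difference in mean score on a 4 to 16 scale.

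The gap cannot be left to the statistical analysis plan. That plan can choose how to analyse a score, but it cannot recover an answer that was not collected at 3 months.

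**Working it through.** **Step 1. Reproduce the scale's stated structure.** Inputs: the item counts and score range in section 8.2.2.

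- Items: 10 + 9 + 7 + 3 = 29, which matches the stated total. No item is left over as a separate symptom question.
- Range: each item scores 1 to 4, so each scale mean lies between 1 and 4. The sum of four scale means runs from 4 × 1 = 4 to 4 × 4 = 16, which matches the stated total. A mean of all 29 items would run from 1 to 4, and a raw sum from 29 to 116, so the stated total must be the sum of the four scale means.

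The outcome is thus a continuous score, and the protocol itself says that it has no cut-off.

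**Step 2. Look for another route to a rate.**

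| Place in protocol | What it holds on faecal incontinence |
|---|---|
| Trial Summary | Listed as a morbidity; no definition |
| 8.2.2 | Quality-of-life scale only; no cut-off |
| 9.1 | Same scale, at 3 months |
| 10.3 | Targeted events; not included |
| 11.1 | Same scale only |
| 14.2.2 | Continuous outcome: difference in means |

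An isolated case might be reported as a serious adverse event, but that is not systematic ascertainment in both arms.

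**Step 3. Compare with the urinary measure.** The ICIQ as described combines symptom items (frequency, amount) with impact. The faecal measure as described has impact scales only. The protocol therefore collects presence and degree of leakage for one kind of incontinence and not for the other.

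**Step 4. Illustration of what a rate could show (assumptions, not protocol findings).** Tear rates of 6% and 4% and 2,600 women per arm are from section 14.1. Two inputs are assumed: that 50% of women with a severe tear have faecal incontinence at 3 months, and that a proportion b of all other women do, with b from 2% to 10%. Complete 3-month response is also assumed.

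Rate = tear rate × 0.5 + (1 − tear rate) × b

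- b = 2%: 0.03 + 0.94 × 0.02 = 4.88%, against 0.02 + 0.96 × 0.02 = 3.92%; difference 0.96 points, about 25 women per arm.
- b = 10%: 0.03 + 0.94 × 0.10 = 12.4%, against 0.02 + 0.96 × 0.10 = 11.6%; difference 0.8 points, about 21 women per arm.

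With z = difference / √[(p₁(1 − p₁) + p₂(1 − p₂)) / 2,600]:

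- b = 2%: 0.0096 / 0.00569 = 1.69, power about 39% at two-sided 5%.
- b = 10%: 0.0080 / 0.00901 = 0.89, power about 14%.

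On these assumptions a binary outcome would probably be inconclusive between arms. Its value is that it can be read as a rate and an absolute difference with a confidence interval.

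**The case against.** The strongest reply is that the instrument is a legitimate choice. The sentence in section 1.1 that cites incontinence goes on to cite reduced quality of life, so the scale measures part of the stated rationale. The objectives in section 2.2.1 do not mention incontinence, sphincter injury is itself the co-primary outcome, and this is one secondary outcome among many. The urinary entry also gives only a total score and no case definition. All of that stands. It supports keeping the quality-of-life scale; it does not supply a rate for an outcome labelled as a morbidity.

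A reader might infer that the questionnaire contains no symptom item at all, so that incontinence can never be derived from it. The protocol does not support that. It gives scale names and item counts, not item wording, and an item within a scale may touch on leakage. What can be said is that no frequency or severity measure is described and no case definition is given. For the same reason, the idea that a woman with low mood and no leakage could score worse than one with mild leakage is unproven.

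A reader might also take the figure of more than 50% as the faecal incontinence rate at 3 months. Section 1.1 gives neither the type of incontinence nor the time point, and places the figure under long-term consequences. It is used above only as an assumption.

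Finally, 2,600 complete questionnaires per arm is optimistic. Section 8.1.1 rates 3-month follow-up of 80 to 95% as amber, and under section 5.3 women without written consent receive no questionnaire.

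**Conclusion.** The point holds as a mismatch between label and measure. Faecal incontinence is a stated 3-month outcome, and the only described instrument consists of four impact scales with no cut-off. As the protocol stands, the trial has a defined way to report a difference in mean quality-of-life score and none to report the number of women affected in each arm.

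This conclusion rests on the protocol's text alone and needs none of the assumed rates. It does not touch the co-primary outcomes, the sample size or the error rates. The gain from a change is interpretability and validity of the outcome, not power; under the assumptions shown, power for the binary outcome would be only about 14% to 39%. The loss is confined to the 3-month time point, since section 2.2.1 foresees long-term follow-up of the cohort, where the question could be asked again. It is a modest, inexpensive improvement that is worth making early.

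**What to change.** Add to the 3-month questionnaire, ahead of the quality-of-life scale, a short question put to every woman on involuntary loss of stool, covering presence and frequency. An established item is preferable to a new one, and its response categories should leave no gap. State a case definition, make faecal incontinence a binary secondary outcome analysed by the model in sections 14.2.1 and 14.2.2, and report the quality-of-life scale as the measure of impact. Bring the Trial Summary and sections 8.2.2, 9.1 and 11.1 into line.

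If the item is not added, relabel the outcome in the Trial Summary and section 8.2.2 as faecal-incontinence-related quality of life, so that no rate is implied.

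Cost: a slightly longer questionnaire, one more binary analysis, and a protocol amendment that may need ethics, HRA and local approval under section 22. Women already past 3 months will lack the item, so the analysis should state the number asked as the denominator.
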